MedDRA Medical Dictionary for Regulatory Activities
MFD Maximum feasible dose
MW151 The investigational product
NIA National Institute on Aging
NOAEL No adverse events level
PIC Proinflammatory cytokine
PK Pharmacokinetic
PPI Protocol Principal Investigator
PSC Protocol Steering Committee
RBC Red blood cell
SAD Single ascending dose
SAE Serious adverse event
SOA Schedule of Activities
TEAE Treatment emergent adverse event
T_{max} Time at maximum drug concentration
T_{1/2} Half-life

WBC White blood cell

SYNOPSIS

Title	A Phase 1a, Double-Blind, Randomized, Placebo-Controlled Single Ascending Dose Study to Evaluate the Safety, Tolerability and Pharmacokinetic Profile of MW151 Administered Orally to Healthy Volunteers
Short Title	Phase 1a SAD Study of MW151
Indication	Radiation-induced cognitive impairment
Rationale	MW151, a small molecule, is being developed for the treatment of cognitive disorders. The development program is based on nonclinical evidence that MW151 improves neurocognitive outcomes in animal models of radiation-induced cognitive impairment, Alzheimer's disease, and other CNS disorders. The present study will provide safety and PK information on single ascending doses to support decisions for continued clinical development.
Objectives	Primary Objective: To assess the safety and tolerability of single ascending doses of MW151 when administered orally to healthy adults Secondary Objective: To assess the PK profile of single ascending doses of MW151 when administered orally to healthy adults

Interventions and Duration	
Subjects will be screened in the 28 days prior to inpatient admission. Subjects will be admitted to the inpatient clinic on the day prior to dosing (Day -1) and will remain in the unit until discharge on Day 3. A follow-up visit will be done on Day 7. A single dose of study drug or placebo will be administered on Day 1.
 
40 healthy adult subjects will be assigned to one of 5 dose cohorts (8 subjects each). The starting dose (10 mg) cohort 1 will include male and female subjects; cohorts 2 – 5 will include only female subjects. Within each cohort, 8 subjects will be randomized to receive MW151 or placebo in the ratio 6:2. According to the dosing scheme each subject will receive a single dose of MW151 or placebo under fasted conditions.
 
1. Starting dose: Dose1 (10 mg)2. Dose2 (20 mg)3. Dose3 (40 mg)4. Dose4 (80 mg)5. Dose5 (160 mg) 
As a safety consideration two sentinel subjects in each cohort will be administered MW151 or placebo in a 1:1 ratio.

-----------------------------------	--

	
Following review of sentinel safety and tolerability data for the first 24 hours of dosing in each cohort (including reported adverse events [AEs], physical examination findings, clinical laboratory results, vital signs, and electrocardiograms [ECGs]), the remaining 6 subjects will be randomized in a 5:1 ratio. Dosing of the remaining subjects in a cohort may proceed after review of sentinel subject safety data collected during the first 24 hours of dosing and determination that no stopping rules are met. The remaining subjects in each cohort will be dosed sequentially, not simultaneously.
 
After the completion of each cohort (Cohorts 1-5), the DSMB will review all available safety data before the dosing of the sentinel subjects of the next cohort.
 
Patients will receive standardized meals during the Inpatient Phase.
 
Data from Cohorts 1-5 will be reviewed in a blinded manner, unless the findings suggest the triggering of a stopping rule, in which case the data for the subjects in question may be unblinded (e.g, if a drug related serious AE [SAE] occurs, identifying whether the subject received MW151 or placebo to determine whether the stopping rule should be triggered).
 
If the data raises questions about safety, the subsequent dose for cohorts may be modified by one of the following:
 
1) repeating the previous dose,2) administering an intermediate dose, or3) terminating dose escalation.
Study Location	1 site located in the United States (US)
Sample Size and Population	40 healthy volunteers who are between the ages of 18-50 years inclusive and weight $\geq 50\text{kg}$, with $\text{BMI} \leq 34 \text{ kg/m}^2$ inclusive will be enrolled into this study. A complete list of all inclusion/exclusion criteria can be found in section 4 of this protocol.

Statistical Considerations	Six actively treated subjects per cohort of 8 (n = 6 MW151, n = 2 placebo) are considered sufficient to provide information on the PK profile and an estimation of safety and tolerability of MW151. Although the sample size is not based on a statistical power calculation, with 30 actively treated subjects the probability of observing at least 1 AE with true frequencies of 0.1%, 1%, 5% and 10% is as follows:										


AE Frequency	N=30	

0.1%	0.030	

1%	0.180	

5%	0.785	

10%	0.958	

		AE Frequency	N=30	0.1%	0.030	1%	0.180	5%	0.785	10%	0.958
AE Frequency	N=30										
0.1%	0.030										
1%	0.180										
5%	0.785										
10%	0.958										

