11.0 DETERMINATION OF SAMPLE SIZE

This trial is designed to investigate the safety, tolerability, and PK properties of the drug MW151 in a dose escalation Phase Ia study. The number of subjects is based upon the need to gain this knowledge in healthy individuals using as few subjects as possible. Since this is the first study of MW151 in humans, there is no prior experience upon which to base estimates of variability for the PK responses to SAD treatment with MW151. No power analysis is conducted but the cohort size is based on accepted standards in similar Phase I studies: 8 subjects per dose with 6 randomly assigned to active drug while the remaining 2 subjects receive placebo. Eight subjects per cohort was deemed sufficient for obtaining an adequate preliminary description of the responses of interest.

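### The Synopsis detection table is wrong in its 1% row: with 30 treated subjects the probability of at least one AE is 0.260, not 0.180

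*Combined protocol and SAP*

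**What the plan says.** The Synopsis, under Statistical Considerations, regards six active subjects per cohort as enough for the PK profile and for a first view of safety and tolerability. It opens the next sentence with a disclaimer, "Although the sample size is not based on a statistical power calculation", and then offers a detection table for the whole active group: "with 30 actively treated subjects the probability of observing at least 1 AE with true frequencies of 0.1%, 1%, 5% and 10"%. The table has a single column, headed N=30:

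| True AE frequency | Printed probability |
|---|---|
| 0.1% | 0.030 |
| 1% | 0.180 |
| 5% | 0.785 |
| 10% | 0.958 |

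Protocol section 9.1 gives no detection probabilities. SAP section 11.0 does not repeat the table and justifies the cohort size differently: "No power analysis is conducted but the cohort size is based on accepted standards in similar Phase I studies".

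**The concern.** All four rows should come from one formula with one n, so any row can be checked against the others. The 1% row does not fit: it is well below what 30 subjects give at that frequency, while its neighbours look right.

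What is at stake is how the safety result is read. The primary objective is safety and tolerability, the safety analysis is descriptive, and this table is the only statement of how likely a study of this size is to reveal an event of a given frequency. A reader who uses it to judge what an absence of some AE among 30 treated subjects means would take a wrong figure from one row in four. The figure could also be carried into later study documents.

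**Working it through.** **Inputs**

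- n = 30 active subjects. The Synopsis says so and the design agrees: 5 cohorts × 6 on MW151 = 30 (Synopsis; protocol section 3; Table 3 in section 4.4.5).
- p = 0.001, 0.01, 0.05 and 0.10, from the same sentence of the Synopsis.
- The event is X ≥ 1, from the words "the probability of observing at least 1 AE".

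**Formula.** With independent subjects who share the same probability p, P(X ≥ 1) = 1 − (1 − p)^n.

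**All four rows at n = 30**

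| p | 1 − (1 − p)^30 | Printed | Agrees? |
|---|---|---|---|
| 0.001 | 1 − 0.999^30 = 0.0296 | 0.030 | yes |
| 0.01 | 1 − 0.99^30 = 1 − 0.7397 = 0.2603 | 0.180 | no |
| 0.05 | 1 − 0.95^30 = 0.7854 | 0.785 | yes |
| 0.10 | 1 − 0.90^30 = 0.9576 | 0.958 | yes |

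Three rows agree to the three decimals printed. The authors therefore used the exact binomial with n = 30, and the discrepancy is confined to the 1% row.

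**Could 0.180 be another quantity at p = 0.01?**

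| Alternative | Result |
|---|---|
| Poisson approximation, 1 − exp(−30 × 0.01) | 0.2592 |
| Expected number of events, 30 × 0.01 | 0.300 |
| Exactly one event, 30 × 0.01 × 0.99^29 | 0.2242 |
| Two or more events, 1 − 0.7397 − 0.2242 | 0.0361 |
| All 40 subjects, 1 − 0.99^40 | 0.3310 |
| One cohort's 6 active subjects, 1 − 0.99^6 | 0.0585 |

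None gives 0.180.

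**Solving backwards.** With p = 0.01, a probability of 0.180 needs n = ln(0.82)/ln(0.99) ≈ 19.7; n = 19 gives 0.1738 and n = 20 gives 0.1821. With n = 30 it needs p = 1 − 0.82^(1/30) ≈ 0.66%. Neither matches the row and column labels.

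**Size of the error.** 0.2603 − 0.1800 = 0.0803, or 8.0 percentage points. The chance of seeing no such event is 0.99^30 = 0.740, against the implied 1 − 0.180 = 0.820.

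**The case against.** The strongest reply is that nothing depends on the figure. The Synopsis says that the sample size does not come from a power calculation, and SAP section 11.0 rests cohort size on Phase I custom. The halting criteria in protocol section 8.1 do not use the figure, nor does any planned analysis. The error is also in the cautious direction, and the message survives it: at either value, an event of 1% frequency is more likely to be missed than seen. All of this is right. It settles the severity as minor, but it does not make the number correct.

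A second reply is that 0.180 may have an innocent origin. A calculation for 20 subjects gives 0.182, which is 0.18 to two decimals, so a value carried over from a different n is possible. The documents do not allow the cause to be established. Whatever it was, a value for 20 subjects is wrong in a column headed N=30 whose other rows use 30.

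A third reply is that the figure appears in one table only, so a misreading of that cell cannot be wholly excluded. Two digits would have to be misread while every neighbouring cell came through intact, which is unlikely. A glance at the source page settles it.

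**Conclusion.** The concern holds. The 1% entry should be 0.260; the printed 0.180 understates the probability by 8.0 percentage points. The result assumes only what the table itself assumes: 30 active subjects treated as one group, independent, with the same AE probability at every dose level. The three rows that reproduce confirm that reading. The error is certain, its effect is minor and its direction is conservative. Sample size, cohorts, halting criteria and analyses are unaffected.

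**What to change.** In the Synopsis, Statistical Considerations, change the 1% row of the N=30 table from 0.180 to 0.260. The other three rows stand. The cost is one cell, which can be corrected at the next protocol amendment or noted in the clinical study report. No SAP text needs to change.

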1 STUDY OBJECTIVES

1.1 *Primary Objectives*

To assess the safety and tolerability of single ascending doses of MW151 when administered orally to healthy adult volunteers.

1.2 *Secondary Objectives*

To assess the PK profile of single ascending doses of MW151 when administered orally to healthy adult volunteers.

2 BACKGROUND

2.1 *Rationale*

Rationale for Study and Disease Indication: Cognitive decline and deterioration of long-term cognitive performance are major side effects of CNS cancer treatment. Brain metastases are the most common CNS malignancies and a common cause of morbidity and mortality in up to 40% of all cancer patients with systemic disease, affecting over 170,000 patients in the US annually (Khuntia et al., 2006; Langer & Mehta, 2005). The main treatment modalities for brain metastases include surgery, whole brain radiation therapy (WBRT) and/or stereotactic radiosurgery. Despite the advantages of WBRT for disease control, cognitive impairment can be seen as early as 3 to 6 months after WBRT, and affects approximately 80-90% of patients, with memory and executive function being the major cognitive domains affected (Greene-Schloesser & Robbins, 2012; Khuntia et al., 2006; Langer & Mehta, 2005). Although the mechanisms underlying the treatment-induced cognitive decline are not completely understood, proinflammatory cytokine overproduction by activated glia after radiation therapy has been consistently implicated in the pathogenesis of WBRT-induced cognitive impairment (Greene- Schloesser & Robbins, 2012; Lumniczky et al., 2017; Warrington et al., 2013). Therefore, therapies that reduce the radiation-induced inflammatory response and subsequent neuronal damage should be explored as a potential adjunctive strategy for reducing WBRT-induced cognitive decline in patients with brain metastases.

More broadly, neuroinflammation, or dysregulated inflammation in the brain, is generally accepted as a contributor to disease susceptibility and pathophysiology progression in a wide range of neurodegenerative disorders associated with cognitive impairment such as Alzheimer's disease (AD) and related dementias, traumatic brain injury (TBI), and seizure disorders (Andreasson et al., 2016; Heneka et al., 2015; Heppner et al., 2015; Van Eldik et al., 2007; Van Eldik et al., 2016). A specific aspect of neuroinflammation, proinflammatory cytokine overproduction from abnormally activated glia, is associated with disease progression and is a druggable process for potential disease modification. However, drugs that target this pathological mechanism are severely underrepresented in the portfolio of candidates being advanced for CNS disorders (Cummings et al., 2018; Fillit et al., 2017).

Our clinical candidate **MW01-2-151SRM (=MW151)**, was developed as part of ongoing attempts to fill this clinical void. MW151 is a novel, CNS-penetrant, orally bioavailable, small molecule drug candidate that selectively suppresses stressor-induced proinflammatory cytokine overproduction with resultant amelioration of synaptic damage and cognitive impairment (Hu et al., 2007). The efficacy and pharmacodynamics (PD) of MW151 are evident across a dozen diverse animal studies where cytokine overproduction is a contributor to pathophysiology progression. MW151 exhibits efficacy, at low doses. It does not bring about immunosuppression or a non-selective anti-inflammatory action. There is no evidence of suppression of basal cytokine levels characteristic of homeostasis. Function at efficacy doses involves restoration to homeostasis after disease or injury induced increases.

Overall, nonclinical efficacy findings and safety profile from nonclinical safety studies suggest that MW151 holds the potential to be useful clinically in treating multiple CNS disorders with cognitive impairment complications. In addition, based on its mechanism of action, MW151 could have disease-modifying effects not only in dementias, but also in a number of acute CNS injuries where proinflammatory cytokine dysregulation is part of the pathophysiology progression mechanism. Finally, MW151 is attractive for development as a stand-alone disease-modifying therapeutic or as part of an armamentarium of therapeutic approaches to alter disease progression in cognitive disorders.

[#] Week 4 AUC values were significantly lower than on Day 1 in this study. Day 1 AUC values in Study 465975 are comparable to Week 4 AUC values in Study 16/301-100P.

[&] A NOAEL was not formally determined in this study. The listed dose level revealed only minimal ECG changes.

CV: cardiovascular

2.3 Supporting Data

Name and Description of Investigational Product: MW01-2-151SRM is the archival ID of the title compound, which is the free base (also referred to by its shortened nickname, MW151), with a molecular weight of 332.40. The MW151 clinical API drug substance (MW151 HCl) is known chemically as 2-(4-(4-methyl-6-phenylpyridazin-3-yl)piperazin-1-yl) pyrimidine dihydrochloride hydrate. It has a molecular formula of C₁₉H₂₀N₆ • 2HCl • H₂O and formula weight of 423.34. MW151 HCl is a white to beige to light yellow powder that is slightly hygroscopic and soluble in water. The

product is available as a capsule filled with the appropriate amount of test substance. In the studies described here, MW151 will refer to the MW151 HCl drug substance unless explicitly stated otherwise.

2.3.1 Nonclinical Studies Pharmacology:

The pharmacological mechanism of action of MW151 is to selectively suppress stressor- induced proinflammatory cytokine overproduction, with resultant amelioration of synaptic damage and cognitive impairment. In *in vitro* based glial activation assays, treatment with MW151 exhibited concentration-dependent suppression of several proinflammatory cytokines typically upregulated by microglia in neurodegenerative disorder, such as IL-1 β and TNF α . In addition, in multiple animal models of CNS diseases, MW151 treatment produced histological and biochemical findings consistent with the ability to significantly attenuate glial activation and proinflammatory cytokine overproduction. The inhibition of glial proinflammatory response correlated well with attenuation of synaptic and behavioral deficits. Importantly, this efficacy is achieved in the absence of any signs of general immunosuppression or non-selective anti- inflammatory action, and no suppression of basal cytokine levels in normal animals.

Preclinical Models of Radiation-Induced Impairment: The therapeutic potential of MW151 for radiation induced cognitive impairment was studied in adult, male Fisher 344 rats subjected to whole-brain irradiation (WBI, 10Gy). Twenty-four hours post-WBI, treatment with once daily 5 mg/kg MW151 i.p. or vehicle control was initiated and continued for 28 days. Proinflammatory activated microglia in the dentate gyrus were assayed at 2 and 9 months post-WBI. Cell proliferation and neurogenesis in the dentate gyrus were assayed at 2 months post-WBI. Novel object recognition and long-term potentiation were assayed at 6 and 9 months post-WBI, respectively. MW151 mitigated radiation-induced neuroinflammation at both early and late time points post-WBI, selectively mitigated the deleterious effects of irradiation on hippocampal neurogenesis, and potently mitigated radiation-induced deficits of novel object recognition consolidation ↓ restoring performance to sham-control levels ↓ and of long-term potentiation induction and maintenance ([Jenrow et al., 2013](#)).

MW151 was also studied in a model of radiation-induced skin injury in C57BL/6 mice, which received focal irradiation (30Gy) on the right hind leg, followed by 5 mg/kg i.p. administration of MW151 three times per week for 21 days, beginning 3, 7, or 14 days post-irradiation. Infiltrating macrophages were persistently increased in irradiated skin and were reduced by MW151 treatment. Irradiated skin also exhibited persistent increases in cells expressing inflammatory cytokines, TGF- β , TNF- β and MMP9. Relative to radiation alone, MW151 administration initiated on days 7 and 14 dramatically reduced expression of these markers in skin from mice that responded to MW151 therapy when assayed at 60–70 days post-irradiation, with skin injury scores showing improvement starting at Day 28 post-irradiation ([Jenrow et al., 2014](#)).

Preclinical Models of Other CNS Disorders/Injury: Complementary pharmacological findings in a variety of nonclinical models of CNS disease and injury indicate that MW151 can effectively limit upregulated glial inflammatory responses and provide neurologic and functional improvements. [Table 2](#) shows a summary of MW151 efficacy and PD in a variety of preclinical animal models.

Table 2: Summary of MW151 Efficacy and Pharmacodynamics (PD) in Preclinical Animal Models

Experimental System	Efficacy and PD Endpoints
Therapeutic radiation (TR)-induced brain injury model (Jenrow et al., 2013 ; PMCID:PMC3673739)	Improved novel object recognition performance; Reduced microglial activation; reduced impairments in neurogenesis.
TR-induced skin injury model (Jenrow et al., 2014 ; PMID:25098729)	Attenuated skin injury; Reduced infiltrating macrophages and proinflammatory cytokine (PIC) up-regulation.
A β Infusion model (Hu et al., 2007 ; PMCID:PMC1868432)	Attenuated cognitive deficits; Suppressed PIC up-regulation; decreased astrocyte and microglial activation; prevented loss of synaptic proteins.
APP/PS1 knock-in model (Bachstetter et al., 2012 ; PMCID:PMC4396836)	Attenuated LTP deficits in hippocampal slices; Repeat long term daily administration attenuated astrocyte and microglial activation; prevented synaptic protein loss; selectively suppressed PIC up-regulation; no effect on A β levels or amyloid plaque burden. Short term daily administration prevented synaptic protein loss; selectively suppressed PIC up-regulation; no effect on A β levels or amyloid plaque burden.
TBI mild diffuse CHI model (Bachstetter et al., 2015 ; PMCID:PMC4396836)	Attenuated cognitive impairments; Suppressed PIC up-regulation dose-dependently; decreased microglia and astrocyte activation.
TBI moderate diffuse CHI model (Lloyd et al., 2008 ; PMCID:PMC2483713)	Attenuated cognitive impairments; Suppressed PIC up-regulation in hippocampus and cortex; attenuated astrocyte activation; reduced neuronal injury.
TBI midline fluid percussion injury model (Bachstetter et al., 2016 ; PMCID:PMC4752278)	Dose-dependent suppression of PIC up-regulation; no effect on microglia cell morphology, proliferation, migration, or phagocytosis.
EAE model of multiple sclerosis (Karpus et al., 2008 ; PMCID:PMC2614915)	Reduced incidence/severity of clinical disease; Reduced spinal cord TNF α levels at peak and CCL2 levels at onset and peak of clinical disease; reduced infiltration of macrophages into the spinal cord at peak clinical disease.
Kainic acid (KA)-induced seizure model (Somera-Molina et al., 2007 ; PMID:17521344)	Protection after early-life seizures; Attenuated PIC up-regulation in hippocampus; reduced astrocyte activation.
KA KA Two-hit model (Somera-Molina et al., 2009 ; PMCID:PMC2739829)	Treatment following early-life KA insult reduced seizure susceptibility and cognitive impairment after a 2 nd KA insult in adults; Reduced proinflammatory cytokine upregulation, microglial & astrocyte activation, and neuronal injury.

Experimental System	Efficacy and PD Endpoints
INCL disease model (Macaulay et al., 2014 ; PMCID:PMC4172802)	In combination with AAV gene therapy, MW151 improved longevity, motor performance in rotorod, and eradicated seizures (chronic admin, 2.5 mg/kg); MW151 alone decreased seizure frequency; In combination with AAV gene therapy, decreased brain atrophy; reduced astrocyte and microglial activation; small effect on proinflammatory cytokine upregulation.
TBI AD Two-hit model (Webster et al., 2015 ; PMCID:PMC4405562)	Reduced cognitive impairment when administered after diffuse TBI in AD mice; Reduced PIC up-regulation and astrocyte activation.
TBI ECS Two-Hit Model (Chraszcz et al., 2010 ; PMCID:PMC2942875)	Treatment following TBI (1 st insult) reduced seizure severity and cognitive impairment after electroconvulsive shock (2 nd insult); Reduced astrocyte and microglial activation, PIC up-regulation and neuronal injury seen after ECS to levels achieved in animals given only TBI insult.

Overall, the nonclinical pharmacology data suggest that MW151 can exert a positive influence on post-injury neurologic outcomes by blunting the brain's intrinsic inflammatory response to CNS insults or disease over a dose range of 0.5 – 10 mg/kg when administered intraperitoneally (i.p.) and 2.5 – 15 mg/kg when administered orally (p.o.). MW151 can suppress the excessive activation of microglia, and their proinflammatory effector responses. The drug is effective at limiting pathophysiological sequelae and secondary neuronal injury in CNS-inflammatory disease relevant animal models, including rodent models of radiation-induced cognitive impairment.

MW151 is moderately well, orally absorbed in rat and dog (F%=23-47%) and distributes into the CNS with brain-plasma ratios > 1. Plasma protein binding of MW151 is high in rat, dog and human with 97.2, 93.9 and 97.1%, respectively.

MW151 appears to be preferentially metabolized by CYP1A2. MW151 has the potential to inhibit CYP2C8 (IC₅₀ = 1.6-12 μM) and to induce CYP3A4 at concentrations ≥ 0.4 μM.

